2.0	offic	reasonably foreseeable that the study will collect information that State or Federal law requires to be reported to other ials (e.g., child or elder abuse), ethically requires action (e.g., suicidal ideation), or is a reportable disease? • Yes • No
		• 2.1
		• If yes, explain below and include a discussion of the reporting requirements in the consent document: We will monitor suicidal ideations using the third item of the Hamilton Depression Scale during each visit to the site. Monitoring for SI will be done at each visit independent of the outcome assessment. The blind rater will be instructed to inform the PI of scores = 3. Subjects with active suicidal ideations with or without a plan, HAMD-24 score = 3, will be excluded from participation. We will call subjects between visits to monitor suicidal ideations. We will encourage participation of their family members in the study who will be encouraged to call the patient and the study staff in case suicidal ideations emerge during the study. In the presence of persistent suicidal ideations, subjects will be discontinued from the study and referred to clinical
		services or to the community for treatment.
3.0	*Ind	icate if any of the following are being obtained and used without any direct contact with study participants. Records (Not medical)
		Human biological specimens
	/	None of the Above
	4	
4.0	*Ind	cate all identifiers that may be accessed or included in the research records for the study:
	4	Names
	•	
	4	Dates
	•	
	4	Age (if over 89 years)
	✓	
	4	Postal Address
	•	Phone Numbers
	✓	Thore Humbers
		Fax Numbers
	4	E-Mail Address
	4	
	4	Social Security Number
	•	
	4	Medical Record Number
	✓	Harallia Dilan Manakana
		Health Plan Numbers
		Account Numbers
		Account Name 19
		License/Certificate Numbers
I	_	

		Vehicle ID Numbers
		Device Identifiers/Serial Numbers
		Web URLS
		IP Address Numbers
		IF Address Numbers
		Biometric Identifiers (including finger and voice prints)
		Facial Photos/Images
		Any Other Unique Identifier (this does not include the code assigned by the investigator to identify the data)
		None of the above

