Randomization and treatment schedule: After all screening and baseline test results are reviewed and eligibility criteria are confirmed, medications will be dispensed if patients continue to meet eligibility criteria and sign the informed consent form. All eligible subjects will be randomized to levomilnacipran or placebo group using a computer-generated random assignment scheme, which assigned subjects in a 1:1 ratio to each group. Randomization will be done prior to subject s being assigned to the groups.

Follow up assessment: The follow up will take place weekly for the first four weeks of treatment, every two weeks for the remainder of the study. Each follow up assessment will include measures of efficacy and safety. The weekly frequency of contact with all subjects will serve as an additional safeguard to monitor worsening of depression, as well as the emergence of side-effects or suicidal ideations.

Study medications and treatment procedures. Subjects will be randomized to: 1) LMIL20-120 mg per day or 2) matching placebo. The allowed range of the drugs according to tolerability and efficacy assessments will be between 20-120 mg per day for LMILN. The dose finding procedures will be only performed in the first four weeks and after that will remain stable until the end of the acute trial, as it worked in our pilot study. We will assess the optimal dose of LMIL based on tolerability and safety in this population. The balance will be maintained between the efficacy and tolerability of medications. If symptoms worsen, the study drug will be tapered and discontinued. Subjects will be referred for clinical care at UCLA or the community. The PI will continue the observation for safety until the appointment is scheduled with the primary psychiatrist. The dose will be titrated according to the titration schedule, including if side-effects are mild or well tolerated and if CGI scores for improvement is 3 or higher. The titration rate is based on the currently recommended titration to achieve the greatest efficacy that may not work for geriatric patients. For that reason, we have safeguards against rapid titration with potential side-effects that will require a slower titration or staying at a lower dose.

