Mild Cognitive Impairment diagnosis. Subjects with mild cognitive impairment will not be excluded. We will use performances between -1.5 and -2 (SD) below age and education norms on one of two memory tests used in our cognitive battery according to a widely accepted practice, and control for it in the analyses.

Randomization and treatment schedule: After all screening and baseline test results are reviewed and eligibility criteria are confirmed by [name]., medications will be dispensed if patients continue to meet eligibility criteria and sign the informed consent form. All eligible subjects will be randomized to levomilnacipran or placebo group using a computer-generated random assignment scheme, which assigned subjects in a 1:1 ratio to each group. Randomization will be done prior to subject sbeing assigned to the groups.

Monitoring of Suicidality.

Assessment and monitoring of suicidal risk will occur at each visit and by phone between visits. We have applied the standard procedures that are required and approved by the UCLA Institutional Review Board. We have employed the same procedures in our ongoing studies of late-life depression since 1995, and have had no suicide attempts among our subjects. We will monitor suicidal ideations using the third item of the Hamilton Depression Scale during each visit to the site. Monitoring for SI will be done at each visit independent of the outcome assessment. The blind rater will be instructed to inform the PI of scores = 3. Subjects with active suicidal ideations with or without a plan, HAMD-24 score = 3, will be excluded from participation. We will call subjects between visits to monitor suicidal ideations. We will encourage participation of their family members in the study who will be encouraged to call the patient and the study staff in case suicidal ideations emerge during the study. In the presence of persistent suicidal ideations, subjects will be discontinued from the study and referred to clinical services or to the community for treatment.

ID: IRB#14-001827

View: NEW 11.2 - Characteristics of Study Population

Warning: Save your work at least every 15 minutes by clicking & Save & or & Continue.

7	k all that apply: 0 to 6 years 7 to 11 years 12 to 17 years
7	7 to 11 years
	·
	12 to 17 years
	12 to 17 years
	17 or younger in California who can consent for themselves - see note below
	17 or younger outside California who can consent for themselves - see note below
*	18 years or older
4	
NOTE	=.

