The MRI scanning procedure requires that you be confined in a small partially enclosed space. Some individuals find this to be uncomfortable and may exhibit symptoms of claustrophobia including nervousness, sweating or other minor discomfort. The sound of the MRI scanner can be quite loud; the subject will be given special ear plugs to minimize the noise. In addition, the magnetism of the machine attracts certain metals; therefore, people with these metals within their bodies (such as pacemakers, infusion pumps, aneurysm clips, metal prostheses, joints, rods, or plates) will be excluded from the study. The metal in dental fillings is less responsive to magnetism and is therefore allowed. The MRI technician will ask you if you have any metals within your body. The subjects will be expected to notify the investigator conducting the study of any metal implants, other than dental fillings. There are no other known side effects resulting from exposure to the MRI scan.

Depression monitoring.

The weekly frequency of contact with all subjects will serve as an additional safeguard to monitor worsening of depression, as well as the emergence of side-effects or suicidal ideations.

- 1. If a patient demonstrates worsening of their symptoms or no response by week 8 or during follow up (i.e., CGI-I score > 3) of treatment, they will be discontinued from the study and referred for appropriate clinical services.
- 2. Suicidal ideations with the HAMD item 3 score of 3 or greater
- 3.The participants will take 20-120 mg of LMIL per day with titration in blinded 40 mg pills prepared by the UCLA pharmacy. The only concomitant psychotropic medication allowed in the trial is lorazepam, 1 of mg or less a day. If patients are not able to tolerate these medications, they will be discontinued from the trial.

The PI will withdraw subjects and discontinue the study treatment if the subject demonstrates worsening symptoms. The study drug will be tapered and discontinued and subjects will be referred for clinical care at UCLA or the community. The PI will continue the observation for safety until the appointment is scheduled with the primary psychiatrist.

Risk/Benefit Analysis

4.0 *RISKS/BENEFIT ANALYSIS: Indicate how the risks to the participants are reasonable in relation to anticipated benefits, if any, to participants and the importance of the knowledge that may reasonably be expected to result from the study:

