Patients will be exposed to potential side effects of the medications both levomilnacipran and lorazepam, which are moderate.

Laboratory and neuropsychiatric tests carry minimal risk. We would like to emphasize that none of our subjects exposed to milnacipran in our pilot study have experienced any elevations in pulse or blood pressure to-date, or ECG changes, although the majority of the subjects had a history of cardiovascular disease and /or hypertension. The subjects with hypertension normalized their blood pressure and had no change in pulse rate with treatment. The risks will also be minimized by weekly frequency of contact with all subjects to serve as an additional safeguard to monitor worsening of depression, as well as the emergence of side-

effects or suicidal ideations. If depression symptoms worsen, the subjects will be given an appropriate referral by the study doctor to psychiatric services provided at UCLA or other mental health clinics within the community; as well as the study doctor will be available to communicate to the subjects primary care physician.

Alternatives

5.0 *Indicate the alternatives to participating in this study.

Check all that apply. All types of studies - Choose not to participate in the study Clinical/Intervention Studies - Receive standard of care instead of participating in the study Clinical/Intervention Studies - Medication, device, or other treatment is available off study Item is Not Applicable (e.g., study of existing data) Other

- 51
- · If "other" was selected, specify.
- •
- 52
- If this is a clinical/intervention study:

Describe the standard of care or activities at UCLA (or study site) that are available to prospective participants who do not enroll in this study. If not applicable to your study, state not applicable (N/A).

The standard of care activities at UCLA include psychotherapy, cognitive behavioral therapy, and other antidepressant medications like Prozac, Zoloft, Pamelor, or electroconvulsive therapy (ECT). The subject may chose to be treated with one or more of these rather than participate in the study. The study doctor is available for questions about alternative therapy for subjects who decide not to enroll in the study. Also, the study drug levomilnacipran is available by prescription without participating in the research.

ID: IRB#14-001827

View: NEW 15.1 - Data & Safety Monitoring Plan

Warning: Save your work at least every 15 minutes by clicking §Save § or §Continue. §

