	information can be found in the attached protocol.	
	•	
2.0	*Provide your assurance that information about serious, unanticipated problems relate incidents and violations) will be reported to the IRB within the time frames specified by	
	Requirements.	
	Agree 🗹 🗹	
	Provide the following information as appropriate to the study:	
3.0	*Are there plans to perform an interim safety analysis?	
	● Yes ○ No	
	• 3.1	
	If yes, describe or indicate where the information can be	
	 found in the attached protocol. Adverse events produced by levomilnacipran may occur. All 	
	- //dverse events produced by leverininacipian may occur. An	

adverse events will be carefully monitored during each visit by using the UKU Side Effect Rating Scale. If any serious medical complication occurs, the PI may discontinue the study medication and may proceed with unblinding the treatment assignment or stopping treatment. We may discover undiagnosed mental and medical conditions in the process of the study, and we will ask for permission by means of a signed Permission to Use Personal Health Information form to report the results of the subjects examination to their primary physician or psychiatrist. An adjustment of the dose of their standing medications may be attempted once seen by their primary care physician. If no improvement occurs or if a prescription of a new medication is required, the study medications will be discontinued.

Discontinuation from the study will be considered if subjects experience:

a. Changes on ECG or in cardiac enzymes indicating cardiac ischemia or a new onset arrhythmia;

b. The development of any severe side-effects on the UKU Side Effect Rating scale rated as 3 or greater.

We will monitor blood pressure and pulse at every visit. We will repeat the ECG once during the trial to ensure safety. If any changes on ECG that signify ischemia occur, we will obtain additional tests of cardiac enzymes to rule out myocardial infarction (MI) (e.g., CK-MB; troponin).

All adverse events will be reported to the subjects and to their primary physicians and the UCLA IRB/ DSMB committee within 10 days of PI�s awareness.

- 1. If a patient demonstrates worsening of their symptoms or no response by week 8 or during follow up (i.e., CGI-I score >3) of treatment, they will be discontinued from the study and referred for appropriate clinical services.

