- 2. Suicidal ideations with the HAMD item 3 score of 3 or greater 3. The participants will take 20-120 mg of LMIL per day with titration in blinded 40 mg pills prepared by the UCLA pharmacy. The only concomitant psychotropic medication allowed in the trial is lorazepam, 1 of mg or less a day. If patients are not able to tolerate it
- 4. These medications, they will be discontinued from the trial. All dropouts will be analyzed by the reason for termination and the reasons will be classified as:
- 1. a) Lack of efficacy; b) Side-effects; c) Lost-to-follow up; d) Hospitalization; e) Death; f) Other
- 2. Relation to the study drug use: a) likely; b) probable; c) unlikely.

All SAE will immediately be reported to the IRB within 3 days or to the Study sponsor Forest Global Drug Safety of all SAE that occurs after informed consent is obtained and if Drug results in:

- Death
- ls an immediate threat to life
- Requires inpatient hospitalization, or prolongation of existing hospitalization
- Results in persistent or significant disability/incapacity
- For all AEs, the PI provide an assessment of causal relationship to the LMIL.

4.0 *Have stopping rules been established for the study?

Yes
No

- 4.1
- If yes, describe or indicate where the information can be found in the attached protocol.
- In the end of the trial after the final procedures, the PI in consultation with the patient's primary physician will decide whether to continue the prescribed medications or switch to another antidepressant based on treatment response and tolerability. If a decision is made to discontinue both medications, they will be stopped and further observation for any withdrawal symptoms will be provided either by the patient's primary physician or the PI for two weeks following the discontinuation.

Discontinuation from the study will be considered if subjects experience:

- a. Changes on ECG or in cardiac enzymes indicating cardiac ischemia or a new onset arrhythmia;
- b. The development of any severe side-effects on the UKU Side Effect Rating scale rated as 3 or greater.

We will monitor blood pressure and pulse at every visit. We will repeat the ECG once during the trial to ensure safety. If any changes on ECG that signify ischemia occur, we will obtain additional tests of cardiac enzymes to rule out myocardial infarction (MI) (e.g., CK-MB; troponin).

5.0 *Are there defined rules for withdrawing participants from study interventions?

Yes No

- 5.1

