- . If yes, describe or indicate where the information can be

found in the attached protocol.

 Subjects have the right to refuse to participate or to withdraw from this research at any time without prejudice, but if they do, they will receive payment only for the time of their participation.

All adverse events that meet the definition of an unanticipated problem will be reported as described below:

- 1. If a patient demonstrates worsening of their symptoms or no response by week 8 or during follow up (i.e., CGI-I score> 3 of treatment, they will be discontinued from the study and referred for appropriate clinical services.
- 2. Suicidal ideations with the HAMD item 3 score of 3 or greater.
 3. The participants will take 20-120 mg of LMIL per day with titration in blinded 40 mg pills prepared by the UCLA pharmacy. The only concomitant psychotropic medication allowed in the trial is lorazepam, 1 of mg or less a day. If patients are not able to tolerate these medications, they will be discontinued from the trial.

The PI will withdraw subjects and discontinue the study treatment if the subject demonstrates worsening symptoms. The study drug will be tapered and discontinued and subjects will be referred for clinical care at UCLA or the community. The PI will continue the observation for safety until the appointment is scheduled with the primary psychiatrist.

All dropouts will be analyzed by the reason for termination and the reasons will be classified as:

1.a) Lack of efficacy; b) Side-effects; c) Lost-to-follow up; d) Hospitalization; e) Death; f) Other 2.Relation to the study drug use: a) likely; b) probable; c) unlikely.

All SAE will immediately reported to the IRB or to the Study sponsor Forest Global Drug Safety of all SAE that occurs. For all AEs, the PI provide an assessment of causal relationship to the LMIL.

ID: IRB#14-001827

View: NEW 16.1 - Payment, Costs, and Injury

Warning: Save your work at least every 15 minutes by clicking Save or Continue.

	icate what the participants will receive for their participation in the study.	
Che	ck all that apply.	
	No payment will be provided	
48	University check	
	Course Credit	
	Cash	
	Gift Cards/Bruincard Deposit	
	Non-Monetary Gifts or Services	
4	Other (including vouchers for parking)	
4		

- . If you selected Non-Monetary Gifts or Services or Other, describe:
- We will offer reimbursement for parking of \$13.00/day for up to \$130.00.

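### After withdrawal for worsening, the PI's safety observation may end once a psychiatric appointment is booked, possibly before the taper ends and before any clinician sees the patient

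*Combined protocol and SAP*

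**What the plan says.** Three sections of the combined protocol and SAP give the same sequence for a patient who worsens.

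- Section 10.1 item 4.0 (study medications and treatment procedures): "If symptoms worsen, the study drug will be tapered and discontinued". Referral to care follows.
- Section 14.1 item 3.0 (depression monitoring) and section 15.2 item 5.1 (withdrawal rules): "The study drug will be tapered and discontinued and subjects will be referred for clinical care at UCLA or the community".
- In all three, the next sentence sets the endpoint: "The PI will continue the observation for safety until the appointment is scheduled with the primary psychiatrist".

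Related text covers neighbouring routes out of the study without that endpoint in the same sentence.

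- The withdrawal lists in 14.1 item 3.0, 15.2 item 3.1 and 15.2 item 5.1 name "If a patient demonstrates worsening of their symptoms or no response by week 8 or during follow up", leading to discontinuation and referral. They also list "Suicidal ideations with the HAMD item 3 score of 3 or greater".
- The risk/benefit text in 14.1 item 4.0 says "If depression symptoms worsen, the subjects will be given an appropriate referral by the study doctor to psychiatric services".
- For suicidality, 11.1 item 6.0 says "In the presence of persistent suicidal ideations, subjects will be discontinued from the study and referred to clinical services or to the community for treatment". Section 9.2 item 2.1 says the same.

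The only fixed period of observation after stopping drug is in 15.2 item 4.1: two weeks, for withdrawal symptoms, by the primary physician or the PI, after a decision taken at the end of the trial.

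**The concern.** Booking an appointment is an administrative step. It shows neither that the taper has finished nor that anyone has assessed the patient. Tying the end of safety observation to it means the study's duty can lapse while the patient is still coming off blinded drug and waiting to be seen.

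The patients concerned are those who have just got worse. Under 10.1 item 4.0 they entered taking no psychotropic medication, and lorazepam is the only one allowed during the trial. A patient on levomilnacipran is therefore tapering off the only antidepressant they have, and a placebo patient already has none. Section 14.1 itself relies on frequent contact as a safeguard against worsening depression and emerging suicidal ideation. On the literal rule, that contact may stop when the need for it is greatest. What is at stake is patient safety alone.

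**Working it through.** No arithmetic applies to the rule itself, so the check sets the texts side by side.

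**Step 1: order of events.** Let W be the day of the withdrawal decision, B the day the appointment is booked, T the day of the last taper dose, and V the day of the first attended visit. A booking precedes its visit, so B is no later than V. The taper starts at or after W, and nothing ties T to B.

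**Step 2: when observation ends.** Under 10.1 item 4.0, 14.1 item 3.0 and 15.2 item 5.1, it ends at B. The time without required PI observation is max(T, V) − B. If the booking is made on the day of withdrawal, B = W and observation may end that day. The wording permits this; it does not require it.

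**Step 3: can the gap be sized?** It would need the taper length and the booking-to-visit interval. Neither is in the documents, nor is an expected number of withdrawals for worsening. No figure can be given for duration or for patients.

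**Step 4: does another safeguard close the gap?**

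| Safeguard | Where | What it provides after early withdrawal |
|---|---|---|
| Ratings at early termination | 10.1 item 4.0, measures and outcomes | An assessment on leaving, not afterwards |
| Primary physician keeps clinical responsibility; referral to one if none is local | 10.1 item 4.0, alternate treatments | Responsibility, but no contact or timing |
| 24-hour pager | 14.1 item 3.0 | Depends on the patient calling |
| Study doctor available to the primary care physician | 14.1 item 4.0 | Contact between doctors, not with the patient |
| Committee psychiatrist for emerging suicidality | 15.2 item 1.1 | Availability; no follow-up assigned |
| Family encouraged to call | 9.2 item 2.1, 11.1 item 6.0 | Depends on the family acting |
| Study calls between visits | 11.1 item 6.0 | Tied to visits; not stated to continue after withdrawal |

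These reduce the risk. None sets a study-initiated contact, or a period of follow-up, after early withdrawal.

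**Step 5: suicidality.** Sections 9.2 item 2.1 and 11.1 item 6.0 state discontinuation and referral only. They do not contain the booking endpoint. Whether such a withdrawal also counts as worsening is left open.

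**The case against.** The strongest reply is that the sentence is a bridge. The study tapers, refers, and keeps watch until the psychiatrist takes over, and the authors may simply have meant until the appointment takes place. A careful PI would probably do more than the text asks. That is fair as to intent, but the text does not say it, and the same wording is used three times.

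A second reply is that detail may lie elsewhere. The attached proposal is not among the documents, and 11.1 item 6.0 refers to IRB-approved suicidality procedures used since 1995 with no suicide attempts among subjects. This stands against any claim that the study has no taper schedule. It does not answer a stated endpoint that is itself too early.

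Several stronger readings are tempting and should not be drawn.

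- *That withdrawn patients are left without any safety net.* The safeguards in the table say otherwise.
- *That the plan contradicts its own two-week rule.* Section 15.2 item 4.1 concerns a choice made after the final procedures, for withdrawal symptoms, and lets the primary physician do the observing. It is a different situation.
- *That the number affected can be read off the plan.* The expected attrition in 10.1 item 4.0 gives 60 − 54 = 6, but that is loss for any reason. Taking the 30–40% in the same item as a response rate would give 60 × (1 − 0.40) = 36 to 60 × (1 − 0.30) = 42 non-responders. The text does not say what that percentage measures, the discontinuation rule uses a CGI-I score above 3, and the taper clause names worsening only.
- *That the booking endpoint is written for suicidality withdrawals.* It is not.
- *That the many mentions of withdrawal show many separate omissions.* Much of that text is repeated.

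**Conclusion.** The point holds for patients withdrawn for worsening. Followed as written, three sections let the PI's safety observation end at booking, which can precede both the end of the ordered taper and any attended care. This rests on taking the word scheduled in its ordinary sense. For suicidal ideation the conclusion is narrower: the documents state discontinuation and referral and leave the observation unstated, which calls for clarification.

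The size is unknown and cannot be derived from the documents. Existing safeguards limit the likely harm. The sample size, power and primary analysis are untouched. It is a modest safety correction, worth making because it is specific and cheap.

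**What to change.** In sections 10.1 item 4.0, 14.1 item 3.0 and 15.2 item 5.1, replace the clause that ends observation at booking with:

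*until the taper is complete and the patient has been seen by the treating clinician, with the existing between-visit safety calls continuing until then; if the patient does not attend or declines contact, observation closes after documented contact attempts and notice to the primary physician.*

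In sections 9.2 item 2.1 and 11.1 item 6.0, state that the same rule applies to patients withdrawn for suicidal ideation.

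Continuing the calls matters: a single call at the close would leave the interval between booking and visit uncovered. No fixed number of weeks is proposed, because the documents give no basis for one.

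The cost is one clause changed in three places, one sentence added in two, and a few extra short calls and attendance checks per withdrawn patient. The study team already orders the taper and already phones patients between visits. The total workload cannot be derived from the documents.
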